6.1.1 Indications for Use

The Pivot Breath Sensor is a breath carbon monoxide monitor intended for single-user use by cigarette smokers to inform the user about how breath carbon monoxide levels are affected by smoking behavior. The device is not intended to be used with other inhaled products.

Figure 1. Pivot Breath Sensor

6.2 LABELING AND PACKAGING

The Pivot Breath Sensor package includes:

- 1 Pivot Breath Sensor
 - 1 USB charging cable
 - 1 Replaceable Mouthpiece
 - 1 Quick Start Guide [REDACTED]
 - 1 Package Insert [REDACTED]
 - 1 Pivot Breath Sensor Educational Booklet [REDACTED]
- [REDACTED]

6.3 PIVOT BREATH SENSOR SUBMITTING A BREATH SAMPLE (SPECIFIC STEPS)

Submitting a breath sample involves the following steps. Instructions can be accessed in multiple locations including the Pivot Breath Sensor's display screen, in the online User Manual [REDACTED], Quick Start Guide, and on the packaging.

1. User presses any button to turn on the Pivot Breath Sensor.
2. User presses and holds the center button on the Pivot Breath Sensor until the sensor beeps once.
3. User takes a deep breath in and holds their breath for 10 seconds.
4. After about 10 seconds, the device beeps 3 times, and the user then will exhale slowly until the sensor vibrates at 12 seconds.
5. The user's CO level will display on the sensor's screen.

A properly submitted breath sample is defined as one that initiates after the third beep prompt and is of at least 6 seconds duration. Breath sensor hardware and firmware is capable of detecting when a breath sample submission starts and stops. The suggested breath sampling regimen is 4 breath samples per day, with samples spread over the course of the day.

The CO Log screen on the Pivot Breath Sensor provides the CO (ppm) value for properly submitted breath samples.

The computation of concentration of CO (ppm) is performed within the Pivot Breath Sensor firmware and the data (CO ppm concentration, time and date) are stored in the Pivot Breath Sensor memory. This data is also stored and visible in the Pivot app when the Pivot Breath Sensor and user's smartphone are paired via Bluetooth Low Energy (BLE). Opening the Pivot app syncs the data to its most updated state, which study staff and participants may access in real-time. User's may also sync their breath sensor data by tapping the breath sensor icon in the upper right corner of the Pivot app and then tapping "Sync Now" in the dropdown menu.

6.4 CO LOG

The CO Log can be accessed from the Pivot Breath Sensor's display screen and shows the most recent exhaled breath CO value in ppm at the top of the screen. The user can view previous values by scrolling within the log (Figure 2).

Values are color coded and can be interpreted by the user with help from the labeling (Figure 3).

Figure 2. CO log on Pivot Breath Sensor

[figure not shown]

Figure 3. Labeling to interpret results

BREATH SAMPLING

Interpreting Your Results

Carbon Monoxide (CO) is a gas found in cigarette smoke.

CO levels in your breath rise with smoking and fall when not smoking.

Each of your breath sample results is displayed on the sensor screen with a color and a number measured in parts per million (ppm).

Interested in learning more about your CO levels and what they mean? Check out our online user manual at: www.pivot.co/user-manual

No amount of smoking is safe.

0-6 ppm
	
Typical levels for a non-smoker, and should be your goal.
 
<small>It is normal to have some CO in your body.</small>

7-9 ppm
	
Borderline values that may be found in smokers and non-smokers.

10+ ppm
	
Typical levels for a smoker.

CO values are also stored in the Pivot app on the participant’s smartphone. When the Pivot Breath Sensor is paired to a user’s phone, his/her CO values and date/time of breath samples populate the Pivot app.

6.5 PIVOT APP

The Pivot app includes educational content, the ability to log cigarettes, set a quit date, create a quit plan, play educational games, watch educational videos, interact with a dedicated human coach via in-app text messaging, view CO breath sample values and trends, learn about and then order NRT, and access the moderated online Pivot

community discussion forum. The educational journey in the Pivot App comprises 4 tracts: Learn, Reduce, Prepare to Quit, and Maintain My Quit, and is designed to accommodate smokers along the spectrum of readiness to quit. Participants may choose to focus on building self-awareness and learn more about their smoking behavior, create and practice their plan to quit or reduce smoking, make a quit attempt, focus on staying quit, or any combination thereof. Accordingly, participants may navigate between tracts as desired to access content most relevant to their goals and needs. [REDACTED] The Pivot app is compatible with iOS and Android phones.

6.6 PIVOT COACHING

Pivot users are assigned a human coach with whom they will work one-on-one over the duration of their use of Pivot (up to one year). Communication between coach and the Pivot user is via asynchronous in-app text messaging. Pivot coaches are tobacco treatment specialists. Coaching is based on cognitive behavioral therapy and uses evidence-based techniques in tobacco cessation such as motivational interviewing, with the aim to help participants reach their goals related to tobacco use. Participants may reach out to their coach whenever and however often they like. The coach will reach out periodically, approximately once per week, during the participant's active use of Pivot.

6.7 PIVOT NICOTINE REPLACEMENT THERAPY (NRT)

Pivot users may order FDA-cleared over-the-counter NRT through the Pivot app. Participants are provided with on-label information about the NRT, must also acknowledge understanding of contraindications. The NRT is free of charge to the participant. There is no out-of-pocket payment by the participant for the NRT. The types of NRT offered in Pivot include nicotine patches (7, 14 and/or 21 mg), nicotine gum (2 or 4 mg), and nicotine lozenges (2 or 4 mg) [REDACTED]. Participants may order patches, gum or lozenges alone as mono-therapy, or they may order patches + gum or patches + lozenges. Participants may order NRT every 2 weeks for up to a 12-week course of NRT. NRT arrives with written instructions/FDA-cleared labeling.

6.8 PIVOT MODERATED ONLINE COMMUNITY

Pivot users may access the moderated online discussion community through the Pivot app. The forum is moderated by a tobacco treatment specialist. The online community forum is a place to give and receive support and advice from others going through the Pivot program.

7. STUDY DESIGN AND OVERVIEW

7.1 STUDY DESIGN

This is a two-arm, parallel-group, non-crossover, single-center pilot randomized

controlled trial conducted with IRB approval enrolling up to 180 subjects who report daily smoking of 5 cigarettes or more. The study will be performed remotely on an ambulatory basis. Participants will be randomized to use either the Pivot (intervention) or QuitGuide (control) app-based smoking cessation program. They will be asked to setup their assigned app on their smartphone and in the case of being assigned to the intervention arm, also set up their Pivot Breath Sensor. Participants will be able to learn about and order up to a 12-week supply of NRT at their discretion. Participants may participate in up to four videocall biovalidation study visits, depending on the smoking status. During these visits, participants provide a breath sample using the Pivot breath sensor, and share their CO ppm results in real-time. The study lasts for 2 years (104 weeks). It is estimated that up to the first 6 months will be primarily focused on active program use and the remaining time in the study will be devoted to passive periodic follow-up. Participants will receive the online study questionnaires via email, from Survey Monkey, at intervals throughout the study.

7.2 STUDY DURATION

The study will run for 2 years (104 weeks).

7.3 STUDY OUTCOMES

- User engagement and retention in the program (number of app opens, number of days with at least one app open, number of weeks with at least one app open)
- Attitudes towards quitting: desire to quit, confidence to quit, difficulty to quit and self-efficacy
- Smoking behavior: quit attempts, change in cigarettes per day (CPD), smoking cessation via 7-and 30-day PPA (self-report and biochemically confirmed), continuous abstinence (self-report and biochemically confirmed), abstinence from all tobacco products, use of NRT
- Participant feedback on the set-up, use experience, design and impact of their assigned smoking cessation program

Outcomes include:

Primary:

- Total app opens in Pivot vs QuitGuide at 12 weeks (3 months)

Secondary:

- Change in expected difficulty in staying quit (participant self-report, scale 1-10) at 2, 4, 8, 12 weeks after enrollment
- Change in confidence levels towards quitting smoking (expected success in quitting, participant self-report, scale 1-10) at 2, 4, 8, 12 weeks after enrollment
- Desire to quit (yes/no) at 4 weeks after enrollment
- Self-reported abstinence (7-day and 30-day PPA) at 6, 8, 12, 26, 52 and 104 weeks after enrollment
- Self-reported abstinence (7-day PPA) at 2 and 4 weeks after enrollment
- Self-reported abstinence from all tobacco products at 6, 8, 12, 26, 52, and 104 weeks after

enrollment

- Biochemically confirmed abstinence at 12, 26, 52, and 104 weeks
 - To be considered biochemically abstinent:
 - Breath CO sample should be less than 10 ppm [16]
- Self-reported continuous abstinence at 26, 52 and 104 weeks, defined as a self-report of smoking no more than five cigarettes from 12 weeks after enrollment
 - 12 weeks is chosen because it allows for a full course of NRT, and it has been standard in studies that include pharmacotherapy for smoking cessation [17]
- Biochemically confirmed continuous abstinence at 26, 52, and 104 weeks, defined as a self-report of smoking no more than five cigarettes from 12 weeks after enrollment, and confirmation on all previous and present biovalidation tests:
 - Breath CO sample should be less than 10 ppm for participant to be considered abstinent [16]
- The proportion of participants who reduced their cigarettes per day (CPD) by $\geq 50\%$ compared to baseline at 4, 12, 26, 52 and 104 weeks
- Number of quit attempts at 4, 12, 26, 52, and 104 weeks (defined as answering ≥ 1 to the following question: “Since you began the study, how many times have you tried to quit smoking where you've gone at least 1 day without smoking a cigarette, even a single puff?”).
- User satisfaction with the smoking cessation program (set-up and getting started with program, recommend to friend, program design, program was useful for quitting, program helped me quit, program helped me stay quit) at 2, 3, 4, 5, 12, 26, 52 and 104 weeks
- Engagement with program, collected weekly during the first 12 weeks after enrollment:
 - Number of times app opened (self-report)
 - Number of days in which app was opened (self-report)
 - Number of weeks in which app was opened (self-report)
- Participant changes in self-efficacy at 6, 12, 26 and 52 weeks
- Participant changes in self-reported health and wellbeing at 26 and 104 weeks
- Self-reported NRT use at 4, 8, 12, 26, 52 and 104 weeks
- Use of other smoking cessation tools (apps, counseling, non-study medications, etc.) at 12, 26, 52, and 104 weeks
- Alcohol use behavior at 12, 26 and 52 weeks (Alcohol Use Disorders Identification Test-Concise or AUDIT-C screening questionnaire, 3 items) [18-20]
- Presence of depressive symptoms screening at 12, 26, and 52 weeks (Center for Epidemiological Studies Depression Scale or CES-D screening questionnaire, 10 items) [11,21-23]
- Living and social environment relating to cigarette smoking at 12, 26 and 52 weeks (live with other adults who smoke, live with romantic partner who smokes, number of close friends who smoke)
- Adverse events at 26, 52 weeks

Eligibility Criteria

The study population comprises current smokers, 21 years of age and above, who own and

regularly use a smartphone and are ready to quit smoking in the next 30 days.

Inclusion Criteria

- 21+ years of age
- Current daily cigarette smokers (at least 5 cigarettes per day) for the past 12 months
- Plans to quit smoking in the next 30 days
- Resident of the United States
- Able to read and comprehend English
- Owns and uses a smartphone compatible with the study app (iPhone 5 and above with operating system iOS 12 and above, or, Android 7.0 and above with operating system Android 7.0 and above)
- Has daily internet access on smartphone
- Comfortable downloading and using smartphone apps
- Willing to sign the Informed Consent Form

Exclusion Criteria

- Pregnancy (self-reported)
- Health contraindications to nicotine patch use (irregular heartbeat, high blood pressure not controlled with medication, heart attack or stroke within the last 2 months, pregnant or breast feeding, skin allergies to adhesive tape or serious skin problems, stomach ulcers, history of seizures)
- Using other smoking cessation support, including apps and/or actively taking medication to quit smoking
- Daily marijuana use
- Residence with another person who is a participant in this study
- Immediate family member is a participant in this study
- Failure to provide contact or collateral information, failure to verify email address, and/or failure to demonstrate videoconference capability
- Participation in a previous study sponsored by Pivot Health Technologies Inc. (formerly Carrot Inc.)

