	
180 adult participants (up to 90 in each arm) who report daily smoking of 5 cigarettes or more. The study will be performed remotely on an ambulatory basis. Participants will be asked to setup and use their assigned program (Pivot for intervention or QuitGuide for control). Both study arms include the option for participants to order FDA-approved nicotine replacement therapy (NRT). The study duration is 104 weeks, with the estimated active time using the program of up to 6 months and the time thereafter as follow-up. Participants will receive online questionnaires at intervals throughout the study and may undergo up to 4 videocall biovalidation study visits in which they provide breath samples using a personal carbon monoxide (CO) breath sensor, which measures CO in exhaled breath.

Data Collection	Data will be collected through participant completion of emailed online questionnaires.
Performance Variables	
Comparison between the two smoking cessation programs on:
 
 • User engagement and retention in the program • Attitudes towards quitting: desire to quit, confidence to quit, self-efficacy and difficulty to stay quit • Smoking behavior: quit attempts, change in cigarettes per day (CPD), smoking cessation via 7-and 30-day PPA (self-report and biochemically confirmed), continuous abstinence (self-report and biochemically confirmed), abstinence from all tobacco products (self-report), use of NRT • Participant feedback on the set-up, use experience, design and impact on their assigned smoking cessation program, and use of other (non-study) smoking cessation tools
Performance Endpoint and Analysis	Change from baseline measurement

Contents

1.	List of Abbreviations	7
2.	Introduction.....	8
2.1	Background	8
2.2	Study Rationale	10
2.3	Potential Risks and Benefits.....	10
2.3.1	Known Potential Risks	10
2.3.2	Known Potential Benefits.....	11
2.3.3	Risk Benefit Assessment	11
3.	Objectives	11
4.	Definitions.....	12
5.	Control – QuitGuide Plus Nicotine Replacement Therapy.....	13
5.1	QuitGuide	13
5.2	Nicotine Replacement Therapy	13
6.	Intervention - Pivot	13
6.1	Pivot Breath Sensor	13
6.1.1	Indications for Use	14
6.2	Labeling and Packaging	14
6.3	Pivot Breath Sensor Submitting a Breath Sample (Specific Steps)	14
6.4	CO Log.....	15
6.5	Pivot App.....	16
6.6	Pivot Coaching	17
6.7	Pivot Nicotine Replacement Therapy (NRT).....	17
6.8	Pivot Moderated Online Community	17
7.	Study Design and Overview	17
7.1	Study Design	17

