1. LIST OF ABBREVIATIONS

CO	Carbon Monoxide
CPD	Cigarettes Per Day
CRF	Case Report Form
FDA	Food and Drug Administration
ITT	Intention To Treat
USB	Universal Serial Bus
IRB	Institutional Review Board
ICF	Informed Consent Form
HCP	Health Care Provider
Ppm	parts per million
NRT	Nicotine Replacement Therapy
RCT	Randomized Controlled Trial

[REDACTED]

Seeking to expand on these learnings both in intervention design and associated outcomes, the Pivot program is a novel digital health intervention for smoking cessation. Pivot comprises a multiphase mobile app, as well as the first Food and Drug Administration (FDA)-cleared personal carbon monoxide (CO) breath sensor, and dedicated human coaching delivered through in-app text messaging. Pivot users may learn about and order NRT in the Pivot app and participate in the Pivot online community. Pivot is designed for individuals with varying levels of readiness to quit and is based on the USCPG for tobacco cessation.

In 2018, we reported results of a nine-day study of 41 participants using only the first phase of Pivot (which at the time was a six-phase program), that included Pivot's FDA-cleared personal CO breath sensor and dedicated one-on-one human coaching using an asynchronous text messaging interface.[12] The focus of the evaluated program phase was to encourage the participant to explore their smoking behavior. Participants completed activities and had the opportunity to log cigarettes and to interact with a coach via text message. More than 80% of participants (34-39 of 41) took ≥ 1 CO breath sample each day, and more than 55% (23-27 of 41) took ≥ 5 samples each day. All 9 in-app activities had completion rates $\geq 80\%$ (33-40 of 41). Response to coach-initiated outreach was also high, with all contacts receiving $\geq 73\%$ (30-39 of 41) response. In matched pair analyses, significant positive changes in mean attitudes toward quitting (scale 1-10) were evident from baseline (T1) to study exit (T2), including increased readiness to quit (T1 mean=6.1, T2 mean=7.4, $P=.005$), lower perceived difficulty of staying quit (T1 mean=3.7, T2 mean=5.6, $P=.001$), and greater expectations of success (T1 mean=4.5, T2 mean=6.5, $P<.001$). At exit, 78% (32/41) of participants reported decreasing the number of cigarettes smoked per day during the study. Participants rated program quality and satisfaction very high (mean ≥ 8 for all items).

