Thereafter, a prospective cohort study evaluated outcomes in 319 adult smokers (intention to treat or ITT cohort) who underwent the full Pivot program; 272 (85.3%) participants completed the end-of-Pivot questionnaire (mean 4.1 months after enrollment) and 288 participants completed the final follow-up questionnaire three months later (mean 7.2 months after enrollment).[13,14] The Pivot program included the Pivot CO breath sensor, smartphone app, and text-based human coaching. The study included individuals along the spectrum of readiness to quit; at study entry most (66.5%, 212/319) were not thinking of quitting smoking in the next 30 days. The study examined participant engagement, changes in attitudes toward quitting smoking, and changes in smoking behavior during, at the end, and three months after active participation in the Pivot program. On average, participants had a mean of 12.4 (SD 7.1) weeks of active program engagement (defined as doing at least 1 of the following per week: completing a breath sample; logging a cigarette; starting or completing a daily activity, challenge or check-in; or messaging one's coach). Repeated measures linear mixed model analyses demonstrated positive changes in attitudes at the end of the pre-quit portion of the program, with increased confidence to quit (4.2 to 7.4, $P<.001$) and decreased expected difficulty maintaining quit (3.1 to 6.8, $P<.001$). The quit attempt rate (i.e., those making ≥ 1 quit attempt lasting ≥ 1 day) was 80.6% (232/288, completer) at final follow-up. At the end of Pivot, 7-day point prevalence abstinence (PPA) rates were 32.0% (102/319, ITT) and 37.5% (102/272, completer) which increased to 34.5% (113/319, ITT) and 39.2%

(113/288, completer), respectively, at final follow-up; 30-day PPA rates were 27.6% (88/319, ITT) and 32.4% (88/272, completer) at the end of Pivot, which increased to 31.3% (100/319, ITT) and 34.7% (100/288, completer), respectively, at final follow-up. Moreover, 30-day PPA rates were comparable among those ready and not ready to quit in the next 30 days at baseline. Of those not achieving abstinence, 25.9% (44/170, completer) achieved $\geq 50\%$ reduction in cigarettes per day (CPD) at the end of the Pivot program.

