11.2 ANALYSIS

In this pilot randomized control study, changes in measurements from baseline to intra-study to exit will be assessed. Participants will serve as their own controls and comparisons will be made to no change. One sample t-test will be used for numerical data. Fisher's Exact or Chi square tests will be used for categorical data. Analyses will be conducted to calculate mean (SD) for normally distributed variables for actual data or mean (SE) for modeled data and median (interquartile range) values in instances of non-normally distributed variables. McNemar test will be used for 2-category match-paired data. Cohen kappa statistic will be used for 3-category match-paired data. Statistical significance is set at $P < .05$. All deviations from the study protocol will be identified, recorded and analyzed.

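### Section 11.2 tests change in confidence, expected difficulty and self-efficacy against no change, so the attitude scales get no between-arm estimate and no baseline adjustment

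*Combined protocol and SAP*

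**What the plan says.** Section 7.3 defines the attitude outcomes as changes at listed times: "Change in confidence levels towards quitting smoking (expected success in quitting, participant self-report, scale 1-10) at 2, 4, 8, 12 weeks after enrollment", "Change in expected difficulty in staying quit (participant self-report, scale 1-10) at 2, 4, 8, 12 weeks after enrollment" and "Participant changes in self-efficacy at 6, 12, 26 and 52 weeks". The synopsis entry for endpoint and analysis reads only "Change from baseline measurement".

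Section 11.2 states that "changes in measurements from baseline to intra-study to exit will be assessed" and that "Participants will serve as their own controls and comparisons will be made to no change". For numerical data it names a one-sample t-test and nothing else. It mentions standard errors for modelled data in passing, but specifies no model, covariate, repeated-measures structure or handling of missing scores.

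Two other places describe a comparison of arms. The synopsis entry on performance variables lists attitudes among the things on which the two programs are to be compared, and Section 2.2 says the trial compares change in attitudes between randomised groups.

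The background (2.1 in the contents list) reports that in the earlier Pivot cohort "Repeated measures linear mixed model analyses demonstrated positive changes in attitudes".

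**The concern.** A one-sample test asks whether scores moved. It does not ask whether they moved more under Pivot than under QuitGuide. Everyone enrolled plans to quit within 30 days and receives a cessation app with optional NRT, so scores may well move in both arms. Change in attitudes is one of the four stated objectives. As written, the randomisation would contribute nothing to the analysis of it.

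Two further weaknesses follow. Without the baseline score in the analysis, any arm difference later formed from change scores would carry avoidable noise and would be exposed to chance baseline imbalance. And with no repeated-measures model, nothing says how a participant who answers at some visits and misses others contributes. Such gaps are foreseeable: Section 7.7 expects 15% attrition, and Section 8.6 sends every questionnaire regardless of whether earlier ones were completed.

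**Working it through.** **1. Is there a figure in the plan to reproduce?** Only for the primary outcome. Section 7.7 assumes 25 (SD 25) against 15 (SD 19) app opens, 80% power and alpha 0.05. The pooled SD is sqrt((25² + 19²)/2) = 22.20, and a two-sided two-sample t calculation gives a total of 156.72, matching the stated 156.7. No SD, correlation or power is given for any attitude scale, so everything below on efficiency rests on assumed values.

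**2. What the planned test can show.** The earlier cohort, which had no control arm, saw confidence rise from 4.2 to 7.4 (3.2 points, P<.001). The same one-sample test applied here could give a result of that kind in each arm while the arm difference was zero. Section 11.2 does not say whether the test is run by arm or on all participants together. Neither choice estimates the difference between programs.

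**3. What baseline adjustment is worth.** Let s0 and s1 be the baseline and follow-up SDs and rho their correlation. Per arm, in large samples:

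- change score: s0² + s1² − 2·rho·s0·s1
- baseline-adjusted: s1²·(1 − rho²)
- difference between the two: (s0 − rho·s1)², which is never negative.

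Adjustment is therefore never less efficient than change scores in large samples. With s0 = s1 the variance ratio is (1 − rho²)/(2(1 − rho)) = (1 + rho)/2, a reduction of (1 − rho)/2:

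| assumed rho | change score (×s²) | adjusted (×s²) | reduction |
|---|---|---|---|
| 0.3 | 1.40 | 0.91 | 35% |
| 0.4 | 1.20 | 0.84 | 30% |
| 0.5 | 1.00 | 0.75 | 25% |
| 0.6 | 0.80 | 0.64 | 20% |
| 0.7 | 0.60 | 0.51 | 15% |
| 0.8 | 0.40 | 0.36 | 10% |

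**4. Sensitivity to unequal SDs.** If s0 = 0.7·s1 (assumed), the ratio is (1 − rho²)/(1.49 − 1.4·rho). The reductions become 15%, 10%, 5% and 1.5% at rho 0.3, 0.4, 0.5 and 0.6. A baseline SD larger than the follow-up SD would raise the gain instead.

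**5. In terms of power (illustration only).** Enrolling 180 with 15% attrition leaves 180 × 0.85 = 153, about 76 per arm. Assume SD 2.5 at both times and a true difference of 1 point at one visit. Power with change scores against baseline adjustment is 55% against 73% at rho 0.3, 69% against 81% at 0.5, 79% against 87% at 0.6, and 97% against 98% at 0.8.

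**6. Direction of the difficulty scale.** The background describes "lower perceived difficulty of staying quit (T1 mean=3.7, T2 mean=5.6" and calls a move from 3.1 to 6.8 in the later cohort a decrease. A higher score there means less difficulty. Sections 7.3 and 9 give only a 1-10 range, so a reader would naturally take a rise as worsening.

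**The case against.** The strongest reply is that these are secondary outcomes in a pilot powered only for app opens, that listing assessment times is not the same as specifying tests, and that defining an outcome as a change does not rule out baseline adjustment. Regressing change on arm and baseline gives the same arm effect as regressing the follow-up score on them. The reference to modelled data shows that some modelling was in mind, and Section 7.5 stratifies on expected difficulty.

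Much of this is fair. It limits what can be claimed, and four stronger readings that a reader might infer should be set aside:

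- *The plan's arm contrast is too noisy by some percentage.* The plan has no arm contrast for these scales. The percentages above are relative to a test that Section 11.2 does not contain.
- *The gain is 20-35%.* That holds only for rho 0.3 to 0.6, equal SDs and a single visit. It is an assumption, not a finding from the documents.
- *The plan runs separate completer tests at each visit.* Section 7.3 gives visit times; visit-by-visit testing is an inference.
- *The sponsor has already used this model.* The earlier mixed model described change over time in a single cohort, with no randomised comparison and no baseline covariate mentioned.

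What remains is enough. A passing reference to modelled data names no model. Stratifying expected difficulty at 5 or below against 6 or above does not adjust for its continuous score, and confidence and self-efficacy are not stratified at all. On scale direction, the anchors may sit in redacted questionnaires, so that note is conditional.

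**Conclusion.** The point holds. For confidence, expected difficulty and self-efficacy, the stated analysis gives no between-arm estimate and no baseline adjustment, while the synopsis and Section 2.2 describe a comparison of the two programs. The missing arm contrast is the main defect; efficiency is the secondary gain.

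The size of that gain is conditional: 10% to 35% lower variance than a one-visit between-arm test of change scores, for assumed rho from 0.8 down to 0.3 with equal SDs. It can be smaller or larger if the SDs differ. This is the gain for a single-visit contrast such as week 12. For an average over four visits, against averaged change scores under compound symmetry, it would be 16% to 56% over the same rho range. The benefit from keeping partly observed participants is additional, is not quantified here, and depends on scores being missing at random.

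The change is worth making. It does not touch the primary outcome.

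**What to change.** In Section 11.2, replace the one-sample test for each of the three scales with a linear mixed model for all scheduled follow-up scores. Fixed effects: arm, visit, arm-by-visit, the continuous baseline score and baseline-by-visit. Use an unstructured within-person covariance. Report the arm difference with its 95% CI at a visit fixed in advance. Week 12 is one candidate, because all three scales are collected then, but the sponsor should choose, since self-efficacy runs to week 52. State the missing-at-random assumption. Within-arm change can still be reported descriptively. This extends the earlier cohort's repeated-measures approach to a randomised comparison.

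In Section 7.3, state that a higher expected-difficulty score means less expected difficulty, if the questionnaire anchors match those of the earlier studies.

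The cost is a few sentences and modest programming. The baseline scores are already needed to form the change scores, so no data are added. The model does have to be written down before the data are seen.
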